PREVALENCE AND INCIDENCE OF ANTIBODIES AGAINST SARS-COV-2 IN CHILDREN AND SCHOOL STAFF MEASURED FOR ONE YEAR IN BELGIUM: A SERO-EPIDEMIOLOGICAL PROSPECTIVE COHORT STUDY – AMENDED PROTOCOL

July 2021

Summary

This protocol amendment describes changes in:

1. Main objective
2. Secondary objectives
3. Study population
4. Questionnaire
5. Testing periods of participants

The **table of changes**, with rationale, the amended protocol, the questions added to the questionnaire and informed consent forms are provided in the following pages. **The sections that have been changed are highlighted in yellow.**

Table of changes

Changes July 2021:

Change / addition	Rational	Affected protocol section

Testing periods: Extension of the study period from 1/9/2021 tot 31/3/2022 with addition of two testing periods (September 2021 and December 2021)
	
The pandemic has not been fully controlled and new waves remain possible. The evolution of the pandemic remains unclear, with the circulation of new variants of concern, a still ongoing vaccination campaign and, so far, no vaccine availability for the paediatric population. With the start of the new school year no vaccine will yet be licensed for use in the under 12 year olds, resulting in primary school children remaining a SARS-CoV-2 infection susceptible population while it is unclear how this will be impacted by a (partially) vaccinated adult population.
 
Further surveillance of the seroprevalence in the paediatric population will inform us on the proportion of children with prior infection. Vaccination in the adult population renders further follow-up of school staff less useful. Similarly, the higher likelihood of vaccination among secondary school pupils making further follow-up of this group also less useful.
 
Keeping the same primary school study population, which is selected to be representative for primary school children of 8-9 year old in Belgium, will enable us to continue providing Belgian paediatric estimates and having a one year cohort including the same children over time. This allows us to provide both seroprevalence point-prevalence estimates and follow changes in incidence. Additionally, we will be able to get more insight in waning immunity and how this is captured by diagnostic tools.
	
3. Methods 3.2. Study design 3.6. Data collection 3.6.1. Data collection procedure 7.6. Study insurance


Target population: Restricted to the primary school pupils
	
By the start of the school year 2021-2022, vaccination age might have been changed for 12 year olds and older. Therefore we limit the study extension to primary school pupils.
 
We do not foresee to include new schools to the study. In case of decreased participation in the school, we will recruit additional pupils up to a maximum of 25 pupils per school to secure a sufficient sample size for the point seroprevalence estimates.
	
2. Objectives 3. Methods 3.2. Study design 3.6. Data collection 3.6.1. Data collection procedure 3.6.3. Laboratory specimen collection, transport and analysis – serological test 3.6.5. Special considerations and circumstances 7. Protection of human subjects and Ethical considerations 7.1. Informed consent 7.6. Study insurance

Additional questions:
	
In the questionnaire that is part of the study and has to be completed by the parents questions on relatives' and (if relevant) child vaccination status will be added.
	
Appendix b: Additional questions to be added at questionnaire for parents

Additional document: New informed consent parents
		
Appendix d: Informatie- en toestemmingsformulier (NL+FR) – separately attached

Changes November 2020:

Change / addition	Rational	Affected protocol section
Target population: Inclusion of school staff	To our knowledge there is little information on the prevalence of SARS-CoV-2 antibodies among school staff (including teaching and non-teaching staff). Quantifying the seroprevalence and incidence in both children and school staff can provide insight in and compare infection circulation within both groups. Changes in incidence over time, as well in the light of more general community transmission data, can add to the interpretation of potential differences or similarities in transmission dynamics in these interrelated populations. Additionally, information on seroprevalence among school staff is valuable for the implementation of and advice on protective measures in the school environment and has the potential to be used to define school staff as risk-group, possibly for the assessment of prioritization of vaccination.	1. Background 2. Objectives 3. Methods 3.1. Study population 3.2. Study design 3.4. Sample size: staff 3.5. Sampling procedure 3.6. Data collection 3.6.1. Data collection procedure 3.6.2. Questionnaire 3.6.3. Laboratory specimen collection, transport and analysis – serological test 3.7. Data analysis 6. Potential Biases and limitations 7. Protection of human subjects and Ethical considerations 7.3. Potential direct benefits for participants and indirect benefits for broader society
Testing periods	Due to delay in the validation of the saliva test procedure for the detection of antibodies the first testing period will take place in December 2020 and the second one in February 2021.	3.6. Data collection 3.6.1. Data collection procedure
Additional questionnaires: 
 Parent registration form: SARS-CoV-2 seroprevalence study among children in Belgium School staff registration form: SARS-CoV-2 seroprevalence study among school staff in Belgium SARS-CoV-2 seroprevalence study among school staff in Belgium: base-line questionnaire SARS-CoV-2 seroprevalence study among school staff in Belgium: follow-up questionnaire 	
The addition of these questionnaires is linked to the expansion of the target group i.e. adding school staff.
 
The registration forms are added to facilitate the collection of personal data necessary for the communication with the parents/guardians of the children and the staff members.
 
This to avoid hand written (difficult to read) contact information.
	
Appendix a: registratie formulier ouders (NL + FR)
 
Appendix a: registratie formulier schoolpersoneel (NL+FR)
 
Appendix a: vragenlijst schoolpersoneel: 1ste contact (NL + FR)
 
Appendix a: vragenlijst schoolpersoneel: 2de en 3de contact (NL +FR)

Additional document: Informed consent school staff.		Appendix c: Informatie- en toestemmingsformulier schoolpersoneel (NL+FR)

Sponsor	Sciensano
Principal investigator	[name], PhD, Epidemiology and public health, Sciensano, and [name], Immune response, Sciensano
Co-investigators and partners	
 • KUL [name], Youth Health Care, Environment and Health • McGill University [name] MSc, Epidemiology, Paediatric Infectious Diseases

SYNOPSIS

Title	PREVALENCE AND INCIDENCE OF ANTIBODIES AGAINST SARS-COV-2 IN CHILDREN AND SCHOOL STAFF FOR ONE YEAR IN BELGIUM: A SERO-EPIDEMIOLOGICAL PROSPECTIVE COHORT STUDY
Acronym	SeroCoBelChild for “Seroprevalence” “Coronavirus” “Belgium” “Child”
Investigators	Sciensano, KUL, McGill
Objectives	
Main objective
 
To determine the prevalence and sero-conversion of antibodies against SARS-CoV-2 in a sample of school-aged children and of school staff (primary and secondary school) and primary school children only in Belgium at different time points.
 
Secondary objectives
 
 • Determine the cumulative incidence of SARS-CoV-2 from baseline to 7 months in the complete sample and 1 year among primary school children • Determine the proportion of asymptomatic infections with SARS-CoV-2 in this sample • Gain insight in the role of COVID-19 infection in household members of children and school staff in this sample • Describe children characteristics and investigate potential risk factors for infection among school-age children • Describe characteristics of school staff and investigate potential risk factors for infection among school staff 
Exploratory objective
 
Will children have to be vaccinated based on incidence of SARS-CoV-2 infection in this sample to create herd immunity?

Duration	12 months, school year 2020-2021 and first semester 2021-2022 . Start September December 2020; 3 sampling periods each spread over max 4 weeks (Oct-Dec 2020, Jan Feb 2020, Apr/May 2021); 2 additional sampling periods for primary school children (September 2021, December 2021)
Design	Prospective observational cohort study
Outcomes	
Primary outcome: seroprevalence of antibodies against SARS-CoV-2 in two age groups of school children and school staff (primary school and lower years of secondary schools) in Belgium.
 
Secondary outcomes:
 
 • SARS-CoV-2 sero-incidence and seroprevalence over time

	
 • Cumulative incidence • Proportion of symptomatic sero-positive cases • Participant characteristics associated with test-positivity
Sample size	Total of 1,640 school-aged children and 820 school staff from 82 Belgian schools (41 primary schools and 41 secondary schools) - 44 primary schools with 820 primary school children for 4 th and 5 th testing period.
Study population	School-aged children and staff of primary and secondary schools in Belgium; For the 4 th and 5 th testing period only primary school children
Intervention - Data collection	Biological sample: Saliva sample for serological testing. Demographic, socio-economic, risk-behaviour, child infection and prevention control and behaviour related data and clinical symptomatology and illness episodes, family members illness episodes, known class and school positive cases and/or outbreaks.

Table of contents

Summary	1
Table of changes	2
1. Background	7
2. Objectives	9
3. Methods	10
3.1. Study Population.....	10
3.2. Study design.....	11
3.3. Sample size: School CHILDREN.....	11
3.4. Sample size: Staff.....	11
3.5. Sampling procedure.....	13
3.6. Data collection	14
3.7. Data analysis	17
4. Expected outcome	19
5. Quality assurance	19
6. Potential Biases and limitations	19
7. Protection of human subjects and Ethical considerations	20
7.1. Informed consent	20
7.2. Potential risks	20
7.3. Potential direct benefits for participants and indirect benefits for broader society.....	20
7.4. Confidentiality	20
7.5. Biological specimen	20
7.6. Study insurance	20
7.7. Data processing and protection (GDPR).....	21
7.8. Distribution of results	21
Appendices	22
References	24

1. Background

Since the beginning of 2020 the world is under the spell of the new SARS-CoV-2 virus which causes high morbidity and mortality in adult populations leading to an overload of healthcare resources on a global scale. As of 27th August 2020, around 24,206,817 confirmed COVID-19 cases have already been reported worldwide since the beginning of the epidemics, among which 826,418 deaths(1). For Belgium this number was 83,030 confirmed cases and 9,879 deaths(2).

Based on studies in China, Iceland, the Netherlands and Italy it seems that children are less affected by SARS-CoV-2 infections and play a lesser role in the dissemination of the SARS-CoV-2 virus (3–7). It is unclear to which extent this is due to lesser exposure or an inherent decreased susceptibility to become infected. In Belgium, until the 27th of August 2020, 5,406 (6.5%) confirmed COVID-19 cases were younger than 20 years of age (1,747 (2.1%) between 0 and 9 years of age and 3,659 (4.4% between 10 and 19 years of age) and Sciensano, the Belgian institute of public health, reported four deaths among the patients younger than 25 years of age (2). The low reported number of cases in children can also be partially explained by the lower testing rates for the diagnosis of acute infection in the paediatric population.

First results of SARS-CoV-2 sero-positivity in Belgium show a seroprevalence among the general population between 4.3% (healthy blood donors between 8 and 10 June) and 6.0% (residual blood samples between 20 and 26 April) and among hospital healthcare workers of 8.8% (representative sample of Belgian hospital healthcare workers between 19 and 24 May)(8). To our knowledge there is no representative data available on seroprevalence among Belgian children and school staff (9).

To get insight in the transmission of SARS-CoV-2 virus in school-aged children, especially in younger or asymptomatic subjects, it is necessary to compile data on infection and past-infection of SARS-CoV-2 virus in the child and (pre-)adolescent population. In early reports, most children were apparently infected within the household (10). In addition, modelling studies of COVID-19 predict that school closures alone would prevent only 2–4% of deaths, much less than other social distancing interventions(11–13). A seroprevalence study following outbreaks in a large school community in Chile showed the highest fraction of infection among teachers, compared to elementary and high school students (14). On the other hand school-based contact-tracing studies found minimal transmission from child or teacher index cases (9,15,16).

Currently studies on rate of infection as well as rate of transmission among children remain scarce. Also the information on SARS-CoV-2 infections among school staff (teachers and others) and the relationship with measured seroprevalence in children is still limited. Nevertheless, such data are important to guide strategies to deal with the current epidemic (e.g. school attendance), and necessary to determine whether children and adolescents will have to be vaccinated in order to achieve herd immunity and to limit the spread of the SARS-CoV-2 virus.

This study will make it possible to better describe the prevalence of circulating antibodies in children and school staff in Belgian primary and secondary schools as well as the incidence of new infections in this subpopulation since they will be followed for 7 months. Additionally, by also questioning household members in the case of the children and by questioning the school staff, we will gain a more in-depth insight in symptomatic COVID-19 disease within households in Belgium, by linking the results of the salivary antibody tests in symptomatic and asymptomatic children with disease information of household members. The study also aims to generate insights in the clinical presentation of the disease among school-aged children and school staff and to evaluate the effect of child behaviour (e.g. participation in outside school activities) on the infection rate among children.

The study will cover all regions¹ in Belgium (Brussels-Capital, Flemish and Walloon Region) and interim data from each wave can guide the Belgian policy makers and CELEVAL (Group of Belgian Experts in charge of COVID-19 related public measures) in their advice on specific COVID-19 related measures for school-age children in order to limit circulation of SARS-CoV-2 in Belgium and to prevent an overload of our healthcare system with a limited societal impact (e.g. school closures). This data might also guide the expert group who will give advice regarding vaccination strategies whether children should be included for vaccination to create herd immunity or not.

¹ A stratified selection of all of all municipalities.

2. Objectives

Main objective

To determine the prevalence and incidence of antibodies against SARS-CoV-2 in a sample of school-aged children and school staff (primary and secondary school) and primary school children only in Belgium at different time points.

Secondary objective

- Determine the cumulative incidence of SARS-CoV-2 from baseline to 7 months in the complete sample and 1 year among primary school children
- Determine the proportion of asymptomatic infections with SARS-CoV-2 in this sample
- Gain insight in the role of COVID-19 infection in household members of children and school staff in this sample
- Describe child characteristics and investigate potential risk factors for infection among school-age children
- Describe characteristics of school staff and investigate potential risk factors for infection among school staff

Exploratory objective

- Will children have to be vaccinated against SARS-CoV-2 to create herd immunity?

3. Methods

The methodology is based on and in line with the methodology as described in the WHO document '*Population-based age-stratified seroepidemiological investigation protocol for COVID-19 virus infection*'(11).

3.1. STUDY POPULATION

The study population includes staff and children of primary and secondary schools. The children belong to two predefined age groups. These two age groups are chosen because studies have shown more pronounced symptoms of infection and disease depending on age and because transmission dynamics also vary by age. Adolescents of 15 year and older will not be included as their symptom patterns resembles more disease pathology of adults. Because of pragmatic and practical reasons we will include primary school children from the 3rd grade (age 8-9) and secondary schoolchildren from the 2nd grade (age 13-14). For primary schools, all school staff, teaching as well as supporting/none-teaching staff (e.g. administrative staff) who has contact with pupils (meaning they are at school at the same time as the pupils are at school), will be included in this study. For secondary schools we decided to include only teaching staff, this because due to present implemented corona-measures in secondary schools, contacts between pupils and none-teaching staff in these schools are at present very limited or not existing. An additional criteria for secondary school teachers to be included in this study is that these have to teach at least also in the 1st or 2nd grade of the secondary school. As teachers often teach in different age-groups and have contacts with colleagues teaching other age-groups, limitation to select teachers teaching dedicated age groups will have no value.

The study sample will be recruited in all Belgian schools including Brussels-Capital, and the Flemish and Walloon Regions (including the German speaking community). School attendance in this age group is high in Belgium (Fédération Wallonie, 2019), for which reason recruitment of school-age children through schools is acceptable.

We do not include children and staff in kindergarten. We assume that transmission dynamics in kindergarten are to some extent similar to those in children in primary school up to the 3rd-4th grade (age 10). The latter group however is easier to approach. Participant inclusion and sample collection in younger children in a school environment without the presence of a direct caregiver would require additional resources.

Following are the eligibility criteria:

Inclusion criteria:

- Children primary schools: any pupil from the 3rd grade (or from the 2nd grade if not enough participants from 3rd grade are available in the selected school) who regularly attend school and is present at school at the first testing period
- Children secondary schools: any pupil from 2nd grade who regularly attend school and is present at school at the first testing period
- Staff primary schools: any teaching or supporting/none-teaching staff (e.g. administrative staff) having contact with pupils and is present at school at the first testing period
- Staff secondary schools: any teaching staff teaching at least also in the 1st or 2nd grade of the secondary school and is present at school at the first testing period
- Prior known SARS-CoV-2 infection does not exclude participation

Exclusion criteria:

- Pupils or staff who refuse to have the saliva sample taken
- For children: being a sibling of a study participant

- A close family member included in the study: only one member per nuclear family will be included in the study
- No informed consent form signed (by parent of legal caregiver) available at the recruitment

3.2. STUDY DESIGN

This study will be set up as a prospective cohort study.

Children and school staff will be recruited at the 1st testing period in the participating school. Samples will be taken within a timeframe of maximum 4 weeks for all the participants.

Parents/legal child caregiver and staff will need to complete a questionnaire at each of the testing moments providing basic socio-demographic characteristics (at baseline only) and risk-behaviour and health characteristics including presence of symptoms during the time since the previous testing period (at each of the testing periods). The questionnaire will be completed ~~by a parent of caregiver~~ through a secured online application during the same week as the collection of a saliva sample. ~~from the child.~~

The study will last 12 months. There will be in total 3 testing periods when data and sample collection will be performed for the total study population; in ~~October~~ December 2020 (Baseline), ~~January~~ February 2021 (M3) and April/May 2021 (M6). There will be a 4th and 5th testing period for primary school pupils only: in September 2021 (M9) and December 2021 (M12).

Saliva samples will be sent to the Sciensano laboratory for analysis. Serological test results will be communicated to the child's parent/legal caregiver by a closed letter through the participating school.

Epidemiological data analysis will be performed and reported after each testing period and at the end of the study.

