3.6.2. Questionnaire

Demographic, socio-economic, risk-behaviour and ~~child~~ infection and control behaviour related data and COVID-19 clinical symptomatology and illness episodes will be collected using a questionnaire at each testing period. Demographic and socio-economic data will only be collected by the baseline questionnaire. Every testing period, information on COVID-19 related symptoms and illness and the contact with (possible) COVID-19 cases will be asked. The questionnaires can be found in the appendix. Questionnaires will be available in French and Dutch.

The questionnaire will be transcribed in LimeSurvey (the data is automatically stored at the secured Sciensano server). Both the French and Dutch version of the questionnaire will be piloted and checked for readability and understanding as well as timing. Adjustments in phrasing can be made to improve the completion of the questionnaire. The questionnaire will be completed online (via computer or tablet/smartphone) by the parents or staff, respectively, during each testing period (background information only at baseline), and will include a pseudonymous ~~child~~ identifier to link the questionnaire data to the result of the biological sample taken from the participant (child or staff) ~~child~~. The web-link to the questionnaire will be provided by the study researchers to the parents of the participating child³ and participating staff members. Families without internet access, will be invited by the school to complete the questionnaire on a school computer or will receive a paper questionnaire through the

³ Given that 87% of the Belgian households have an internet connection (federal government economy) we opted to using an online questionnaire, and the questionnaire can also be completed on a smartphone.

school which they can complete and return to the school (under closed envelop). The school will deliver these paper questionnaires to the study researchers who will enter the data in the database.

If questionnaires are missing 1 week after closure of a testing period, a reminder will be sent to the (parents of) participants.

Basic data from the participating schools will be collected. Prior to the different sample periods, the schools will be contacted, periodical school closures and known SARS-CoV-2 outbreaks at the schools will be recorded.

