3.7. DATA ANALYSIS

The analysis will be descriptive for the primary objective. Variables will be described as proportions with a 95% Confidence Interval (95%CI). Several epidemiological parameters/effect measures will be calculated with a 95%CI.

Among others:

- Seroprevalence of SARS-CoV-2: number of children/ number of school staff in whom specific SARS-CoV-2 antibodies was detected by ELISA / total number of children/staff tested.
- SARS-CoV-2 seroconversion rate: Number of children/ number of school staff in whom presence of specific antibodies was detected by ELISA during any of the follow-up tests with a previous sample showing no specific antibody / total number of children/staff followed-up with a baseline negative serum sample, during the study period of 7 months.
- Cumulative incidence
- Incidence rates (using both the total population and the population excluding the non-susceptible from the prior sero-survey testing period)
- Proportion of asymptomatic cases
- Proportion of symptomatic episodes amongst positives versus negatives

A flow diagram of the participants will be created reflecting number of participants approached, eligible and included. The statistical analysis will account for the small differences in sampling probability due to the study design by using specialized procedures for complex (survey) sampling..

For the secondary objectives, uni- and multivariate analysis will be performed assessing risk, protective and predictive factors associated with sero-positivity among children and among staff. Relative risk of sero-positivity in function of specific risk factors (prior to analysis a directed acyclic graphs (DAG) will be constructed and risk factors will be analysed using Poisson regression and effect

measures will be re-calculated and presented as absolute risks and risk differences with their CI). Models will be assessed for presence of confounders and interaction.

When tables will be presented e.g. test positives versus test negatives at the end of the study, no p-values will be presented comparing differences in basic characteristics to avoid chance-findings.

A sensitivity analysis will be performed to estimate bias resulting from the imperfect accuracy of serology testing. If needed other sensitivity analysis will be performed and selection bias will be assessed. Depending on the amount of missing data imputation will be used.

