7.8. DISTRIBUTION OF RESULTS

The study protocol will be registered at [Clinicaltrials.gov](https://clinicaltrials.gov).

Anonymous study results should be made accessible and available as soon as possible after every testing period and at the end of the study to public health authorities involved in management of the COVID-19 epidemic in Belgium. This can be done through a policy brief or presentation. Sciensano will coordinate the distribution of results. These results will be also published on the relevant websites of these institutions.

The general public will also be informed regarding these anonymous results through press communications. This will be done by the communication departments of Sciensano and of the study partners.

Scientific peer-reviewed publications (possible short publication, regular paper) will be prepared to add to the body of evidence and availability for the global scientific community and public health decision makers.

Appendices

a. Questionnaires:

- Parents: 1ste contact,
- Parents: 2nd and 3rd contact,
- Schools: baseline
- Schools: 2nd and 3rd testing period
- Parent registration form
- School staff registration form
- School staff: baseline
- School staff: 2nd and 3rd testing period

b. Additional questions to be added at questionnaire for parents at 4th and 5th testing period

1. Werd uw kind gevaccineerd tegen het coronavirus (COVID-19)?

- Ja, mijn kind kreeg één dosis van een vaccin
- Ja, mijn kind kreeg twee dosissen van een vaccin
- Neen, mijn kind kreeg nog geen vaccin

1.1. Indien optie 1: Datum van de eerste dosis:

1.2. Indien optie 2: Datum van de tweede dosis:

Indien u de exacte datum van de vaccinatie niet kent, kan u aangeven wanneer uw kind ongeveer werd gevaccineerd.

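### The symptom recall window follows the study round, not the participant's own last sample, which risks overstating the proportion of asymptomatic infections

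*Combined protocol and SAP*

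**What the plan says.** Section 3.2 has parents and staff report "presence of symptoms during the time since the previous testing period (at each of the testing periods". Section 3.6.2 repeats that symptoms are collected each round but gives no window: "Every testing period, information on COVID-19 related symptoms and illness and the contact with (possible) COVID-19 cases will be asked". It adds "The questionnaires can be found in the appendix", but the text of those forms is not in the document supplied.

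Section 3.7 defines seroconversion as a positive result at any follow-up test after a previous negative sample. It does not require the two samples to come from adjacent rounds. The same section lists "Proportion of asymptomatic cases" with no numerator, denominator, symptom window or rule for missed rounds. Section 2 makes the proportion of asymptomatic infections a secondary objective. The synopsis and section 4 list the proportion of symptomatic seropositive cases as a secondary outcome.

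Section 3.2 describes recruitment at the first testing period only. The July 2021 table of changes foresees later entry: "In case of decreased participation in the school, we will recruit additional pupils up to a maximum of 25 pupils per school". On background data, section 3.6.2 says "Demographic and socio-economic data will only be collected by the baseline questionnaire". The Appendices list a parent form called "Parents: 1ste contact", a follow-up parent form, and item b, "Additional questions to be added at questionnaire for parents at 4th and 5th testing period", which covers vaccination only. Nothing says which form or recall window applies to a late entrant.

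**The concern.** A new positive can be called asymptomatic only if symptoms were asked about over the whole period in which the infection could have occurred. Under the plan, the serological interval belongs to the person and the symptom window belongs to the study calendar. The two agree for anyone who completes every round and can differ for everyone else.

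Take a pupil who is negative in December 2020, misses both the sample and the questionnaire in February 2021, and is positive in April/May 2021. Under section 3.2 this pupil is asked about symptoms since February only, so a symptomatic illness in January is never recorded. A pupil first tested in September 2021 may carry antibodies from well before the previous round, because section 3.1 does not exclude prior infection.

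The gap also touches staff and secondary pupils who miss a round, and first-sample positives at baseline, for whom no previous testing period exists. Unasked symptoms can only raise the apparent asymptomatic proportion.

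**Working it through.** The plan gives no expected asymptomatic proportion and no sample size for this objective, so there is no figure to reproduce. The check has two steps.

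**Step 1: share of the infection interval not asked about.**

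Inputs from section 3.2: rounds in December 2020, February 2021, April/May 2021, September 2021 and December 2021. With January 2020 as month 1, I place these at 12, 14, 16.5, 21 and 24. For the two extension rounds I assume that the section 3.7 definition, written for 7 months, carries over. For late entrants I assume risk from March 2020 (month 3).

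Formula: u = (interval − recall window) / interval. The interval runs from the participant's own last sample, or from March 2020 at a first test.

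| Case | Interval (months) | Recall window | Not asked | u |
|---|---|---|---|---|
| Skipped February 2021 | 16.5 − 12 = 4.5 | 2.5 | 2.0 | 44% |
| Skipped April/May 2021 | 21 − 14 = 7 | 4.5 | 2.5 | 36% |
| Skipped September 2021 | 24 − 16.5 = 7.5 | 3 | 4.5 | 60% |
| First tested September 2021 | 21 − 3 = 18 | 4.5 | 13.5 | 75% |
| First tested December 2021 | 24 − 3 = 21 | 3 | 18 | 86% |

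On the protocol's own labels (M0, M3, M6, M9, M12), skipping one round leaves 3 of 6 months unasked, or 50%, in each case.

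**Step 2: effect on the asymptomatic proportion.**

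Formula: apparent = p + (1 − p) × s × u, where p is the true proportion and s is the share of analysed positives with a mismatched window. The formula assumes uniform infection over the interval. It also assumes that a positive with no symptoms reported in the latest window is classed as asymptomatic, and that no unrelated symptoms are reported in that window. The documents give none of p, s or the classification rule.

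| p | s | Apparent, u = 0.44 | Apparent, u = 0.75 |
|---|---|---|---|
| 30% | 5% | 31.5% | 32.6% |
| 30% | 10% | 33.1% | 35.3% |
| 30% | 30% | 39.2% | 45.8% |
| 50% | 5% | 51.1% | 51.9% |
| 50% | 10% | 52.2% | 53.8% |
| 50% | 30% | 56.6% | 61.3% |

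Example: 0.30 + 0.70 × 0.10 × 0.75 = 0.3525. The smallest skipped-round case is 0.50 × 0.05 × 0.36 = 0.9 points. If all the mismatched positives were first tested in December 2021, p = 30% and s = 10% would give 0.70 × 0.10 × 0.86 = 6.0 points.

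If the window ran from the participant's own last sample (or from the start of the epidemic at a first test), u would be 0 and the apparent proportion would equal p.

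**The case against.** The strongest reply is that section 3.2 gives a one-clause summary and the forms themselves cannot be read here. The summary cannot be literal for every form, because at baseline there is no previous testing period. This stands: the actual wording may already be better than the protocol text, although the protocol does not say so.

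Second, missing a saliva sample is not the same as missing the questionnaire. Section 3.6.2 has parents answer online, with a reminder, and a parent who answered every round leaves no gap. This also stands, and it limits the problem to rounds where both were missed. Section 3.2 places the two in the same week, so they may well be missed together.

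Third, late entrants have no earlier negative sample and cannot count as seroconverters. That is correct. They matter only if the proportion is taken among all seropositives, which is how the secondary outcome in section 4 reads.

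Fourth, the bias is small beside the sampling error. At the planning prevalence, 6% of 820 is about 49 positives, and the 95% half-width around an assumed 40% is 1.96 × √(0.4 × 0.6 / 49) = 0.137, about 14 points before any design effect. This is fair for a single round. The bias, however, does not shrink as positives accumulate: at an assumed 20% prevalence (164 positives) the half-width is about 7.5 points.

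A reader might go further and infer that returning and late-joining children are certainly counted as asymptomatic. The documents do not support this. Section 3.7 never defines an asymptomatic case, and it leaves room for imputation and sensitivity analyses. A reader might also infer that late entrants have no socio-demographic data and fall out of the risk-factor models. That is not supported either. A first-contact parent form exists, and the November 2020 table of changes and the Appendices use first contact and baseline for the same staff form, so a new entrant may well receive it.

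**Conclusion.** The concern holds as a mismatch between two stated rules: symptom recall by round, and seroconversion from the person's own last negative sample. No passage reconciles them for missed rounds or late entry. After one fully missed round, about 36% to 60% of the interval goes unasked.

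If these positives are treated as symptom-free, the asymptomatic proportion is overstated by roughly 1 to 5 points when 5% to 10% of positives are affected. At 30% affected, the overstatement is 6.6 to 15.8 points (56.6% against a true 50%, up to 45.8% against a true 30%). The direction is clear. The size rests wholly on assumed values of p, s and u, uniform infection over time, and a classification rule that the plan does not state. Only symptomatic infections in the unasked months are misclassified.

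This affects a descriptive secondary objective and a related secondary outcome. It should be corrected because the correction is nearly free.

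**What to change.** **Sections 3.2 and 3.6.2.** Set the recall window to the time since the participant's own last study sample and, at a first test, to the time since the start of the epidemic. State that pupils first enrolled at period 4 or 5 complete the existing first-contact parent form plus the questions in appendix b.

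**Section 3.7.** Define an asymptomatic case. Combine all questionnaires completed since the last negative sample, and classify positives with an uncovered interval as symptom status unknown. Base the main proportion on seroconverters with full coverage, and report first-sample positives separately.

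**Cost.** This takes a wording change in an online form, reuse of an existing form, and one analysis rule. A few participants face a longer recall period, and the main estimate rests on slightly fewer positives. The amendment predates periods 4 and 5, so the new window can apply to both; for periods 1 to 3 only the analysis rule can help. If the forms already work this way, a sentence in 3.2 and the definition in 3.7 are enough.
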